CTOT-15 is designed to be a first step in providing the potential benefits of an immunosuppressive regimen based on an agent other than a CNI to this underserved patient population. Currently, SPK recipients have no alternatives to CNIs for maintenance immunotherapy. As a result, immunosuppressive protocols remain dependent on these agents despite the long term nephrotoxicity and beta cell toxicity associated with these agents. Furthermore, as abatacept, a precursor of NULOJIX® (belatacept), has been shown effective for treatment of the autoimmune disease psoriasis, we believe that NULOJIX® (belatacept) may offer unique benefits to pancreas transplant recipients with type I diabetes mellitus by acting to control the autoimmune response.

CTOT-15 will also incorporate a battery of mechanistic assays that are designed to be integrated with many of the assays being performed as part of CTOTC-02 and CTOT-16. These assays compare the effects of the belatacept-based regimen on protective antiviral immunity, alloimmunity, and autoimmunity. The study design allows us to focus on how these two different classes of immunosuppressive agents affect memory responses including those that predate the transplant and those arising from homeostatic lymphocyte repopulation.

Over the last two decades, the short-term results of organ transplantation have improved steadily in large part due to the introduction of increasingly potent immunosuppressants. Calcineurin inhibitors (CNI), such as cyclosporine and tacrolimus, form the backbone of the vast majority of all immunosuppressive regimens currently used in abdominal organ transplantation (www.srtr.org). The success of these CNI-based regimens is demonstrated by the ever-decreasing incidence of acute rejection and the ever-improving 1-year graft survival following de novo renal and extra-renal transplantation. Disappointingly, this improvement in short-term outcomes has not resulted in concomitant improvements in long-term outcomes¹,². The major factors limiting the long-term survival of transplanted kidneys and kidney transplant recipients are the near universal development of

interstitial fibrosis and tubular atrophy (IFTA)³ and the extremely high incidence of cardiovascular disease in transplant recipients. This is particularly true for patients with type 1 diabetes undergoing simultaneous kidney and pancreas transplantation.

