3 RATIONALE FOR SELECTION OF STUDY POPULATION

CTOT-15 will study individuals undergoing *de novo* simultaneous pancreas and kidney transplantation (SPK) from a deceased organ donor. This study will test the hypothesis that a regimen of induction with Thymoglobulin® (anti-thymocyte globulin- Rabbit) followed by maintenance with NULOJIX® (belatacept) and minimization or withdrawal of calcineurin inhibitors (CNI) will result in comparable rates of rejection and superior renal function as compared with a tacrolimus-based maintenance immunosuppressive regimen in recipients of SPK.

A transplanted pancreas can elicit both an alloimmune response and an autoimmune response from the recipient. Individuals undergoing SPK transplantation are presumed to be at greater risk of immunologic allograft injury than those that undergo kidney transplant alone; thus, they are treated with more aggressive CNI-based immunosuppressive regimens. However, the population that presents for SPK is also at higher risk for the morbidities associated with CNI due to the consequences of long-standing diabetes. This proposal is an attempt to extend the potential benefits of reduced CNI exposure, facilitated by maintenance therapy with NULOJIX® (belatacept), to recipients of SPK transplantation.

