12.5 Markers of Autoimmunity

The CTOT-15 study will explore the impact of the autoimmune response on graft function following pancreas transplantation. The hypothesis that is being tested is that markers of recurrent autoimmune disease will correlate with graft loss as defined by a return to insulin dependence. The details of the assay will be worked out at the time of the samples are available based on the needs of the study and technology. The assays for the cellular response against autoantigens are being developed in collaboration with the laboratory of [name] (Benaroya Insititute, Seattle). This work will compliment the current work conducted in the Clinical Islet Transplantation (CIT) consortium.

Whole blood will be collected, and peripheral blood mononuclear cells (PBMCs) and serum will be isolated from CTOT-15 participants at baseline, days 28 and 84, weeks 28, 36, and 52. In addition, these samples will be collected at the time of suspected rejection, prior to initiating therapy. The samples will be stored at the University of California, San Francisco for future analysis of markers of autoimmunity.

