13.2.3 Mechanistic Assay Analyses

The primary mechanistic objective of CTOT studies is to identify and elucidate pathophysiologic and genetic mechanisms that are associated with allograft rejection and how these associations may evolve over time and/or differ between therapeutic treatments. In this study, the principal objectives of the mechanistic analyses of data from subjects receiving kidney or pancreas transplants will include assessment of the association between treatment (i.e., belatacept vs. tacrolimus maintenance) and renal function, incidence of viral infection and autoimmunity.

Ten mechanistic assays are described in Section 12. There are from 1 to 3 separate correlations or tests desired for each assay category and these are described in Table 8. The analysis numbers in the table refer to the following 10 assays:

- 1. Intracellular cytokine staining and viral phenotyping
- 2. Flow cytometry
- 3. Protein Assays
- 4. Gene expression, mRNA profiling
- 5. Anti-HLA alloantibodies and non-HLA antibodies
- 6. Autoimmunity markers
- 7. Genomics (gene polymorphisms)
- 8. Renal histology
- 9. Renal immunohistochemistry
- 10. Pancreatic histology
- 11. Viral testing (viral load determination)

Depending on the scale of measurement of the endpoints, the amount of missing data, and the questions of interest, exploratory data analysis (EDA) and/or statistical hypothesis testing and modeling will used. Given the small sample sizes (n=30 in each of 2 treatment arms), modeling and testing will generally be restricted to the continuous endpoints where the focus will be testing for treatment and time effects on repeated measures of the endpoints. These types of analyses will have sufficient sample sizes to make reasonable inferences; e.g., repeated measures ANCOVA tests for differences in gene expression in the treatment arms, over 5 assessment times would have to following degrees of freedom for the their error terms: treatment df = 58; time df = 238, time × treatment = 238.

Page 87 of 104

Analysis No.	Effector cells, antibodies, or markers (see Sect. 12)	Meas. Scale	Assay	Objective	Analysis Method ¹
1a	Virus-specific T- cell subpopulations	Continuous. (cell counts)	Cytokine staining + PCR	Correlation with viral loads detected with PCR, by visits and treatment arm	Spearman Rank Correlation Coeff., by visit and treatment group; treatment x time plots; tables of summary stats.

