5b	Anti-HLA and non-Anti-HLA antibodies	Binary (present absent)	Luminex	Examine prevalence patterns of HLA- A, B, C, DR, DQα, DQβ, DPβ, and anti- MICA	Contingency tables and CMH tests by marker ; treatment x time plots; tables of prevalence means and stderrs by treatment arm and visit
5c	De Novo donor- specific anti-HLA antibodies	Continuous	Luminex	Correlation with eGFR, and biopsy findings (if enough are done), by visits and treatment arm	Spearman Rank Correlation Coeff., by visit and treatment group; treatment x time plots; tables of summary stats.
6	Markers of recurrent autoimmune disease following pancreas transplant	Continuous	TBD	Compare distributions of anti-GAD, anti- insulin and anti- IA2 between subjects with AR and no AR	EDA using graphical and tabular summaries of the data in AR vs. non-AR within and between subjects.
7	Genomic analysis of polymorphisms (SNPs) in cytokine genes	Binary	TBD	Determine if differences in cytokine genetic polymorphisms are associated with AR	Logistic regression analysis for additive and recessive hypotheses; wherein, the predictors are the numbers (0,1,2,) of recessive alleles for each SNP.

Page 89 of 104

Analysis No.	Effector cells, antibodies, or markers (see Sect. 12)	Meas. Scale	Assay	Objective	Analysis Method ¹
7	Morphological markers in biospsied kidney tissue + CD4 markers	Continuous + binary (present/absent)	Trichrome, H&E, and CD4 staining	Correlation with visit 1 – week 52 changes in Banff scores and corresponding changes in several morphometric features of the grafts	Spearman Rank Correlation Coeff., by visit and treatment group; tables of summary stats.
9	Renal markers of fibrosis and inflammation	Binary (present/ absent)	Immuno- histochemical staining	Compare genomic, proteomic, cytokine profiles in subjects with/without the renal markers	Tables of summary statistics to compare within-subject changes in markers and profiles between visit 1 and week 52.
10	Morphological markers in biospsied pancreatic tissue + CD4 markers	Continuous + binary (present/absent)	Trichrome, H&E	Correlation with visit 1 – week 52 changes in Banff scores and corresponding changes in several morphometric features of the grafts	Spearman Rank Correlation Coeff., by visit and treatment group; tables of summary stats.

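### Table 10 row 6, the only planned analysis of the autoimmunity markers, leaves out both the insulin-dependence outcome of Section 12.5 and the arm comparison of Section 13.2.3

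*Combined protocol and SAP*

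**What the plan says.** Section 12.5 gives the hypothesis for the autoimmunity assay: "markers of recurrent autoimmune disease will correlate with graft loss as defined by a return to insulin dependence". Samples of mononuclear cells and serum are scheduled at baseline, days 28 and 84, and weeks 28, 36 and 52, and again when rejection is suspected.

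Section 13.2.3 opens with an aim shared across the network: "The primary mechanistic objective of CTOT studies is to identify and elucidate pathophysiologic and genetic mechanisms that are associated with allograft rejection". It then gives this study's own principal mechanistic objectives, which include "assessment of the association between treatment (i.e., belatacept vs. tacrolimus maintenance) and renal function, incidence of viral infection and autoimmunity". Section 2.1 says much the same: "These assays compare the effects of the belatacept-based regimen on protective antiviral immunity, alloimmunity, and autoimmunity".

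In Table 10 these markers appear as the object of analysis only in row 6. Its objective is "Compare distributions of anti-GAD, anti- insulin and anti- IA2 between subjects with AR and no AR" and its method is "EDA using graphical and tabular summaries of the data in AR vs. non-AR within and between subjects". The measurement scale is continuous and the assay is still to be determined.

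**The concern.** The row that is supposed to deliver the autoimmunity analysis uses a different outcome from the hypothesis and has no treatment factor. If it is followed as written, the trial will report how the markers differ by rejection status. It will not report whether they go with return to insulin, or whether they differ between belatacept and tacrolimus maintenance. Sections 13.7 and 13.8 label every analysis outside the plan as ad hoc. A later analysis of the hypothesis in Section 12.5 would therefore carry that label, while a contrast that does not address it would be reported as planned.

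**Working it through.** The plan gives no sample size, power or alpha for this analysis, so there is no figure to reproduce. The main check is a comparison of texts, followed by a feasibility calculation for the two missing comparisons.

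**1. Outcome.**
- Section 12.5: graft loss, meaning return to insulin dependence.
- Row 6: acute rejection, yes or no.
- The Study Definitions treat these as different events. Pancreas acute rejection is a histological finding on a biopsy done for clinical suspicion, or suspected rejection treated without a biopsy. Pancreas graft failure is a return to insulin, or the start of oral agents, for more than 30 days.
- The Banff 2011 pancreas scheme in the same section puts recurrent autoimmune diabetes under islet pathology (category 7), apart from T-cell-mediated rejection (category 3).
- Section 3 also separates the two processes: "A transplanted pancreas can elicit both an alloimmune response and an autoimmune response from the recipient".

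Rejection status is therefore not the outcome named in Section 12.5.

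**2. Treatment arm.**
- Section 13.2.3 has treatment against autoimmunity as an objective.
- Row 6 has no arm in its objective or its method.
- Rows 1a to 1c, 2a, 2b, 4b, 5a to 5c, 11a and 11b do bring in the arm. Rows 2a, 4b, 5a and 11b specify repeated-measures ANCOVA.

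**3. Which rejection.** Row 6 does not say whose rejection counts. Table 9 defines its acute rejection endpoint for the kidney or the pancreas. On that reading, a subject with kidney rejection and a working pancreas falls in the rejection group.

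**4. Data available.** 60 subjects × 6 scheduled times = 360 sample sets, plus those taken for suspected rejection. This is a nominal maximum, because the reduced follow-up schedule (Appendix 4) lists no marker samples. Section 10.3 has graft loss assessed at every visit.

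**5. Feasibility.** Two-sample t test, two-sided alpha 0.05, power 80%, df = n1 + n2 − 2, noncentrality = d / √(1/n1 + 1/n2), solved for d in SD units.
- Arms, 30 against 30: d = 0.74. The normal approximation is (1.960 + 0.842) × √(2/30) = 2.802 × 0.258 = 0.72.
- Return to insulin against none, arms pooled. The documents give no expected count, so I assume a range:

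| Events of 60 (assumed) | Detectable difference (SD) |
|---|---|
| 3 | 1.69 |
| 6 | 1.23 |
| 9 | 1.03 |
| 12 | 0.92 |
| 15 | 0.85 |

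An arm comparison could detect a moderately large difference. A comparison by return to insulin could detect only large ones, so it should be descriptive.

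**The case against.** Four points can be made for the plan.

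- **The rejection contrast has a stated purpose.** It serves the network-wide objective on rejection. This stands: row 6 is incomplete, not pointless, and its own objective and method agree with each other.
- **An arm comparison may already be covered.** For continuous mechanistic endpoints Section 13.2.3 says "the focus will be testing for treatment and time effects on repeated measures of the endpoints", and row 6 is marked continuous. This stands in part. The sentence is qualified as a general tendency, while row 6 specifies descriptive summaries by rejection status. The text permits an arm comparison but does not plan one, and it does nothing for the outcome in Section 12.5.
- **The details are deferred.** Section 12.5 defers the details of the assay, and row 6 leaves only the assay open. The outcome and the contrast are fixed, so this does not answer the point.
- **The stakes are low.** The markers are not in the Section 1.6 list of mechanistic secondary endpoints, the row is descriptive, and footnote 1 to Table 10 makes tests and models depend on adequate sample size. This stands, and it limits the weight of the point.

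A reader might go further and infer that autoimmune failures must fall in the group without rejection, so that the planned contrast would be empty or even reversed. The documents do not support that. The pancreas definition counts suspected rejection treated empirically without a biopsy, so an autoimmune recurrence managed that way would be classed as rejection. No event rates are given from which to say how many subjects would fall on either side, and nothing in the plan points to a reversal.

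**Conclusion.** The mismatch is in the text. The hypothesis in Section 12.5 has no planned analysis, and the arm-level objective in Section 13.2.3 has no specific one for these markers. A reader might infer that the marker data could not answer either question. That is too strong: most of what is needed is already scheduled, and the general sentence leaves room for the arm comparison. What is missing is the commitment in row 6.

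The primary endpoint and the listed secondary endpoints are unaffected. The detectable differences in the working (0.74 SD between arms; 0.85 to 1.69 SD by return to insulin) rest on complete data, a simple two-group comparison and, for the second, assumed event counts. They show what is feasible and do not measure the size of an error. The point is worth correcting because the correction is cheap and the alternative is an ad hoc label on the analysis that the protocol says it is testing.

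**What to change.** Keep rejection against no rejection in row 6 as a descriptive contrast, and state which organ's rejection counts. Add two analyses.

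- **(a) By return to insulin dependence, as worded in Section 12.5.** Compare each marker, as change from the pre-transplant sample, between subjects with and without the event. Use only samples drawn before the event and compare at matched visits, so that subjects whose series stops at an event are not set against others followed to week 52. Label it descriptive and exploratory. If the Graft Failure-Pancreas definition is used instead, say that it also counts oral agents and requires more than 30 days.
- **(b) By arm and visit.** Use the repeated-measures method of rows 4b and 5a, subject to footnote 1 on sample size. State that marker values will be missing once a subject moves to reduced follow-up.

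If only the rejection contrast is wanted, reword Sections 12.5 and 13.2.3 to match it.

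The cost is a change to the plan's wording and a little extra analysis, with no new samples. Analysis (a) assumes that the date of return to insulin can be taken from the medication and graft-loss records, and it may rest on few events.

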12.6 Genomics

We will isolate and save a DNA sample from each consented patient potentially to use in genomic analysis of polymorphisms for cytokine genes. There are several such gene polymorphisms that have been associated with increased risk of poor outcome post-transplant. While our goal is not to test the association between various genetic polymorphisms and graft outcome, it is possible that once our study is complete there may be questions regarding whether our results are independent of such polymorphisms and that it would be prudent to maintain small samples for analysis should such questions arise.

As already noted, prior studies using belatacept have been associated with acute rejection rates higher than standard therapy and the current study intends to optimize its use to minimize rejection or other toxicities. Analysis of gene polymorphisms in recipients may provide insight into allograft outcomes. Recently, polymorphisms in the CTLA4 gene have been described and associated with transplant outcome²⁵. We will analyze these polymorphisms as well as other others related to transplant outcomes²⁶. DNA will be isolated from the donor and recipient prior to treatment and subsequently analyzed. These results will be analyzed in terms of the primary and secondary endpoints of the study.

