13.2 Endpoint Assessments

13.2.1 Primary Clinical Endpoint

The primary endpoint will be the week-52 eGFR. Mean eGFR of the belatacept group will be compared to the mean eGFR of the tacrolimus reference group within a mixed models repeated measures (MMRM) framework , wherein repeated measures of eGFR at weeks 4, 12, 28, 36 and 52 will be modeled as a linear function of time (and perhaps other baseline covariates) in the 2 treatment groups. At week-52, a contrast will be made between the eGFR mean of the belatacept group and the eGFR mean of the tacrolimus group. ANCOVA assumptions will be evaluated graphically via standard residual analyses. If the assumptions fail, a suitable transformation (e.g., natural logarithms) will be found and the data will be reanalyzed on the transformed scale. Results will be reported with p-values associated with the F-test for each contrast and the corresponding mean treatment differences with two-sided 95% confidence intervals. All tests of significance will be two-tailed at the 0.05 level.

Estimating the contrasts within the repeated measures framework will provide treatment comparisons that are robust to subject dropout bias as long as the dropout pattern is missing at random²⁷. Data are missing at random whenever the "missingness" mechanism is a function of observable relationships among the nonmissing responses and covariates. Using the methods of Ma et al.²⁸, we will evaluate the MAR assumption in the data prior to implementing the MMRM analysis. If the MAR assumption fails, we will consider more robust alternatives (e.g., pattern mixture modeling)²⁹.

A number of studies have shown RMANCOVA to be superior to analyses of completers or of data with LOCF imputations³⁰. Nonetheless, we will conduct 2 related sensitivity analyses: (1) replace the missing week-52 values with the corresponding nonmissing week 36 values of each subject, dropping anyone who is missing both week-36 and week-52 and perform the ANCOVA as currently specified; (2) include only the completers in the ANCOVA analysis (i.e., exclude all dropouts). The sensitivity analyses will be included as additional secondary analyses.

13.2.2 Secondary Clinical Endpoints

The secondary endpoints are defined in Protocol section 1.5.

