The protocol defines 28 secondary clinical endpoints. The endpoints are to be computed and summarized by treatment and, in a few cases, by day/week and treatment. With the exception of specific AEs and lab parameters, proportions or means will be estimated for each treatment arm and tested for treatment differences through the use of a statistical model. The particular model to be used depends on the scale of measurement of the endpoint. The accompanying table lists each endpoint and its measurement scale (continuous, dichotomous, and ordinal). All tests of significance in all analyses will be made at the 0.05 level.

Dichotomous measures of prevalence and incidence will be analyzed with log-binomial regression models, wherein treatment effects will be estimated as relative risk ratios; the reference group will be the tacrolimus-thymoglobulin subjects. The log-binomial model (rather than logistic regression) is applied for prevalence and incidence analyses because model-based estimates of relative risk (RR) are both more desirable and appropriate for non-Poisson events that are expected to occur more commonly than in 10% of the cases. In such cases, logistic regression-based odds ratio (OR) estimates are poor estimators of the relative risk³¹,³²,³³,³⁴. It may be appropriate to treat some of the dichotomous outcomes as censored data; if this is the case, we will obtain RR estimates by fitting Cox regression models to the data³⁵.

The single ordinal secondary outcome variable (Banff cell-mediated AR score) will be analyzed in a proportional odds model³⁶ which may include additional covariates and interaction terms, as appropriate.

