1b	Virus-specific T- cell subpopulations	Binary	Cytokine staining + PCR	Comparison of prevalence of each T-cell type by visits and treatment arm	Contingency tables and Cochran Mantel Haenszel (CMH) tests
1c	Virus-specific T- cell subpopulations	Continuous. (cell counts)	Cytokine staining + PCR	Correlation with B-cell counts, NK cell counts, dendritic cell counts by visit and treatment arm	Spearman Rank Correlation Coeff., by visit and treatment group; treatment x time plots; tables of summary stats.
2a	Donor-reactive T- cell subpopulations	Continuous. (cell counts)	Flow Cytometry	Look for treatment arm differences in counts, over time	Random Effects repeated measures ANCOVA (RMANCOVA); treatment x time plots and random coefficients models and plots; tables of means and standard errors
2b	Donor-reactive T- cell subpopulations	Continuous. (cell counts)	Flow Cytometry	Correlation with eGFR, de novo anti-donor HLA and biopsy findings, by visits and treatment arm	Spearman Rank Correlation Coeff., by visit and treatment group; treatment x time plots; tables of summary stats.
3	Protein Assays				
4a	Gene expression data for > 128 markers	Continuous	Real -time PCR	Identify associations between specific mRNAs and the occurrence of AKI, CHI, CIT, and fibrosis, by visit pooled over trt	EDA: various graphical comparisons and descriptive statistics (by visit if there are enough occurrences of AKI, CKI, CIT, and/or fibrosis

¹ Statistical tests (e.g., t-tests) and statistical models (e.g., ANOVA) will only be performed if sample sizes are adequate

Page 88 of 104

Analysis No.	Effector cells, antibodies, or markers (see Sect. 12)	Meas. Scale	Assay	Objective	Analysis Method ¹
4b	Gene expression data for > 128 markers	Continuous	Real -time PCR	Look for evidence of treatment differences in the occurrence of each marker over time	Separate RMANCOVAs for each marker; treatment x time plots; tables of means and standard errors by marker, treatment arm, and visit
5a	Anti-HLA and non-Anti-HLA antibodies	Continuous	Luminex	Characterize the occurrence of HLA-A, B, C, DR, DQ α , DQ β , DP β , and anti- MICA, by treatment arm and visit	Separate RMANCOVAs for each ab.; treatment x time plots; tables of means and standard errors by antibody, treatment arm, and visit

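### The genomics row of Table 10 gives the recessive hypothesis the additive predictor (0, 1, 2), so the recessive test as written duplicates the additive one and has reduced power for a recessive effect

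*Combined protocol and SAP*

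**What the plan says.** The relevant entry is the genomics row of Table 10 (section 13.2.3), the first of two rows numbered 7. Its objective is: "Determine if differences in cytokine genetic polymorphisms are associated with AR". Its method is: "Logistic regression analysis for additive and recessive hypotheses; wherein, the predictors are the numbers (0,1,2,) of recessive alleles for each SNP". Neither that row nor section 12.6 defines another genetic variable. Section 12.6 commits to the work in general terms ("We will analyze these polymorphisms as well as other others related to transplant outcomes") and does not discuss coding.

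Three other statements set the context:

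- Section 13.2.3 gives the size of the data set, "Given the small sample sizes (n=30 in each of 2 treatment arms", so 60 subjects in total. It adds that "modeling and testing will generally be restricted to the continuous endpoints".
- A footnote to the Analysis Method column of Table 10 says: "Statistical tests (e.g., t-tests) and statistical models (e.g., ANOVA) will only be performed if sample sizes are adequate".
- Section 12.6 also says that testing genetic associations with graft outcome is not the study's goal, and that the DNA is stored for possible use.

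**The concern.** Additive and recessive are different statements about the heterozygote. Under the additive model on the log-odds scale, one copy moves the subject halfway from no copies to two. Under the recessive model, one copy does nothing. The difference between the two analyses lies entirely in how the single-copy group is scored, and the plan scores it 1 on a 0-to-2 scale for both.

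If an analyst programs the row as it stands, the result reported as recessive is the additive result under a second label. A true recessive association is then diluted, because heterozygotes are treated as partly at risk. Sections 13.7 and 13.8 label analyses outside the plan as ad hoc, so a recessive indicator introduced after the data are seen could attract that label or a dispute over it.

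**Working it through.** The plan states no power, allele frequency or effect size for this analysis, so there is no figure of its own to reproduce.

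**Inputs from the documents.** There are 60 subjects (section 13.2.3), a yes/no outcome of acute rejection, and the predictor coding in Table 10. The 0.05 level comes from section 13.2.2 ("All tests of significance in all analyses will be made at the 0.05 level") and two-sidedness from section 13.2.1 ("All tests of significance will be two-tailed at the 0.05 level"). Neither is stated for the genomics row itself, so both are carried over as assumptions.

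**Inputs assumed.** These are the recessive-allele frequency q, Hardy-Weinberg proportions, and the rejection risks by genotype.

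**Step 1: are the two codings the same variable?** Let G be the allele count and R = 1 if G = 2, otherwise 0. Then Var(G) = 2q(1−q), Var(R) = q²(1−q²), and Cov(G,R) = 2q² − 2q·q² = 2q²(1−q). The squared correlation is

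4q⁴(1−q)² / [2q(1−q) · q²(1−q²)] = 2q/(1+q).

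This is 0.6/1.3 = 0.46 at q = 0.3, 0.8/1.4 = 0.57 at q = 0.4 and 1.0/1.5 = 0.67 at q = 0.5. The codings are well short of interchangeable.

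**Step 2: what does the count fit when the truth is recessive?** Take a constructed data set with 200, 200 and 100 subjects carrying 0, 1 and 2 copies, and 40 rejections in each group. The observed risks are 20%, 20% and 40%.

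| Predictor | Fitted risk, 0 copies | 1 copy | 2 copies |
|---|---|---|---|
| Count 0, 1, 2 | 17.4% | 25.1% | 34.9% |
| Indicator of two copies | 20% | 20% | 40% |

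The count invents a heterozygote effect and understates the homozygote effect. The indicator recovers the pattern exactly, with log-odds ratio ln[(0.4/0.6)/(0.2/0.8)] = 0.981.

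**Step 3: power with 60 subjects.** The truth is taken as recessive with 15% risk for 0 or 1 copies. The test is a simulated 1-df likelihood-ratio test at 0.05. A homozygote risk of 60% is an odds ratio of (0.60/0.40)/(0.15/0.85) = 8.5.

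| Homozygote effect (assumed) | q | Count | Indicator | Loss (points) |
|---|---|---|---|---|
| Odds ratio 2 | 0.3 to 0.5 | 9–15% | 10–16% | about 1 |
| Odds ratio 3 | 0.3 to 0.5 | 15–30% | 20–36% | about 5–6 |
| 60% risk (odds ratio 8.5) | 0.3 | 41% | 60% | 19 |
| 60% risk | 0.4 | 64% | 78% | 14 |
| 60% risk | 0.5 | 81% | 90% | 9 |

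**Step 4: sensitivity to the assumptions.** A score test with base risk 20% and homozygote risk 50% gives, for count against indicator, 12% v 25% at q = 0.2, 22% v 38% at q = 0.3, 34% v 50% at q = 0.4 and 46% v 61% at q = 0.5. That is a loss of about 13 to 17 points. With 70% homozygote risk the loss is about 10 to 27 points over the same frequencies.

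The expected number of homozygotes, 60q², is 2.4 at q = 0.2, 5.4 at q = 0.3 and 15 at q = 0.5. For less common alleles there is little to work with under any coding.

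**The case against.** The strongest reply is that the row is a one-cell summary. It names the recessive hypothesis, and its bracketed 0, 1, 2 could describe the genotype data from which each model's term is built. It could also mean a three-level class variable. As a class, the recessive pattern can be fitted: in the Step 2 data it gives a heterozygote effect of 0 and the same homozygote log-odds of 0.981. Any analyst holding the genotypes can form the two-copy indicator.

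Part of this stands. A reader might infer that the recessive test will never be carried out. The documents do not support that: the hypothesis is named, the data allow the test, and a competent analyst may well code it properly. A reader might also infer that power for a recessive effect is lost. It is reduced: at 60% homozygote risk the count still has 41% to 81% power.

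The rest does not rescue the wording. The row does not leave the predictor blank; it says what the predictors are, and what it describes is a count. A class variable is not mentioned. Its 2-df test would be neither of the two named tests, and it is less powerful than the indicator for a recessive effect (30% v 38% at q = 0.3, base risk 20%, homozygote risk 50%).

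The footnote on adequate sample sizes, the general restriction to continuous endpoints and the disclaimer in section 12.6 decide whether the analysis is run and how much weight it carries. They do not say how it is coded.

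**Conclusion.** The coding is wrong as written for one of the two named hypotheses. Taken literally, the recessive analysis repeats the additive analysis and has reduced power for a truly recessive effect.

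The size of the loss depends on assumptions that the documents cannot settle. With 60 subjects, 15% base risk and allele frequency 0.3 to 0.5, it is about 1 to 6 points at odds ratios of 2 to 3 and about 9 to 19 points at 60% homozygote risk. The larger losses need a very large single-polymorphism effect. At modest effects neither coding gives a usable test.

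The point is minor. It concerns one exploratory mechanistic analysis that runs only if the sample is judged adequate. The treatment comparison, the primary endpoint and the secondary clinical endpoints are untouched.

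**What to change.** Replace the predictor clause in the genomics row of Table 10 with: *additive hypothesis: predictor = number of recessive alleles (0, 1, 2); recessive hypothesis: predictor = 1 if two recessive alleles, 0 otherwise.* The same edit could say how the two tests per polymorphism will be read together.

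The cost is one sentence. It needs no new data, assays or visits, and it should be settled before the genotypes are analysed against rejection.
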